AVAPS-AE is a mode of therapy (Philips Resironics Inc, Monroeville, Pa) with potential advantages over the currently established modes of non-invasive positive pressure ventilation (CPAP and bilevel therapy). This mode of therapy incorporates AVAPS (automated adjustable IPAP setting to maintain target ventilation with a settable rate of change), Auto EPAP and Auto Back up Rate. We believe that these automated parameters will allow better nocturnal ventilatory control to offset the differing elastic and resistive loads imposed by changes in body position during sleep. Furthermore, AVAPS-AE will counter the changing ventilatory requirements due to alterations in lung volumes and airway resistance during different stages of sleep. In summary, the AVAPS-AE mode will enable automatic adjustment in response to ventilatory changes throughout the night. The device platform used in this study with the AVAPS-AE feature is in the BiPAP A40 platform. This device uses existing modes of therapy, therapy features, and algorithms as that which have been previously cleared by the Food and Drug Administration (FDA) (K121623).

III. Study Objectives/Endpoints

Specific aim #1: Evaluate the effects of novel application of Averaged Volume Assured Pressure Support (AVAPS-AE) therapy on time to (# of days) emergent and non-emergent healthcare utilization in patients with sleep-disordered breathing who are hospitalized with co-morbid COPD.

Specific aim #2: Evaluate the effects of novel application of Averaged Volume Assured Pressure Support (AVAPS-AE) therapy on the number of emergent and non-emergent healthcare utilization over 6 months;

A Pilot, Multi-Center, Randomized, Open-Label, Parallel Group Study to Assess the Effects of a Novel Application of Averaged Volume Assured Pressure Support Ventilation (AVAPS-AE) therapy on Re-hospitalization in Patients with Sleep-Disordered Breathing with co-morbid COPD.

Confidential

costs related to re-hospitalization; number of visits to physician offices or emergency rooms, and health-related quality of life (disease-specific and general HR-QOL measures).

Primary Endpoints

Composite end-point of time to occurrence of emergent healthcare utilization (such as re-hospitalization, unscheduled physician office visits, urgent care visits or emergency room visits).

Secondary Endpoints:

1. Healthcare Costs
2. Change in quality of life (SF-36) at 30 and 60-days
3. Change in quality of life (FOSQ) at 30 and 60-days

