- One week Device Adherence Assessment (Intervention Group)

During the first 2-7 business days post discharge, research staff will evaluate participant's device adherence via remote download. Participants with poor adherence to AVAPS-AE at home (adequate adherence defined as \geq 4 hours of use on at least 5 of the first 7 nights) will not be included in the "per-protocol analysis" (Such participants will, however, be considered in the intention to treat analysis). Per the investigators discretion, the device setting parameters may be adjusted at this time.

- Weekly Phone Follow-ups (Initial 30 days only):

Phone calls will be made weekly (\pm 2 business days) by the study coordinator to assess mask interface issues (Intervention group) and encourage adherence to AVAPS-AE (Intervention group) and medications (both intervention and SOC group). If participants require an additional visit related to issues noted above, this visit may occur either in the home or as an office to the study site.

- Day 30

At 30 days (\pm 2 business days) post discharge, participants in both Intervention and SOC groups will receive a phone call to determine if they had been admitted to this hospital, or had an unplanned visit to a physician's office or emergency room. Participants will be asked to complete FOSQ and SF-36 questionnaires. Participants will be given the option of completing the questionnaires verbally via phone call or completing handwritten copies and returned via direct mail. Postage paid return envelopes will be provided to participants who elect to complete and return the surveys by mail.

- Day 60

On day 60 (\pm 2 business days), participants in both Intervention and SOC groups will receive a phone call to determine if they had been admitted to this hospital, or had an unplanned visit to a physician's office or emergency room. Participants will be asked to complete a final FOSQ and SF-36 questionnaire. Participants will be given the option of completing the questionnaires verbally via phone call or completing handwritten copies and returned via direct mail. Postage paid return envelopes will be provided to participants who elect to complete and return the surveys by mail. Participants in both

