A Pilot, Multi-Center, Randomized, Open-Label, Parallel Group Study to Assess the Effects of a Novel Application of Averaged Volume Assured Pressure Support Ventilation (AVAPS-AE) therapy on Re-hospitalization in Patients with Sleep-Disordered Breathing with co-morbid COPD.

Confidential

Physical Exam	X		
Medication Assessment	X		
Bedside Spirometry	X		
Room Air SpO2 assesment	X		
Anthropometric measurements	X		
Stop -Bang Questionnaire	X		
20 minute PAP Wash-in	X		
QOL questionnaires (FOSQ and SF-36)	X	X	X
Charleston Co-Morbidity Index	X		
Overnight Portable Sleep Test	X		
Randomization	X		
Device Set up training/Mask fitting	X		
1 week PAP adherence assessment (Treatment Group only)		X	
Weekly phone calls to promote PAP and medication adherence		X	
30 day Healthcare utilization assessment and questionnaire Phone Call		X	
60 day Healthcare utilization assessment and questionnaire Phone call		X	
Transition Plan			X
Optional Registry			X

VII. Statistical Analysis

The method described by Cook and Lawless will be used to handle repeated hospitalizations, physician office visits, or emergency room visits in patients who may or may not also have a terminal event. All repeated hospitalizations that occur in patients will be counted. We will use the count-approach and the gap-time approach, described by Cook and Lawless because we are interested in studying event occurrence rates in the two groups as well as the time to occurrence of events. Analysis will be performed for both 30- and 60-days. Actuarial costs will be assessed in patients belonging to both the intervention and usual care arm. Unadjusted comparisons of these costs will be made by independent t-tests or non-parametric equivalent. Differences will be adjusted for potential confounders and other covariates in

A Pilot, Multi-Center, Randomized, Open-Label, Parallel Group Study to Assess the Effects of a Novel Application of Averaged Volume Assured Pressure Support Ventilation (AVAPS-AE) therapy on Re-hospitalization in Patients with Sleep-Disordered Breathing with co-morbid COPD.

Confidential

multivariate regression models, to include age, gender, race, body mass index, baseline severity of COPD, AVAPS-AE and medication adherence. Biologically plausible effect modification will be evaluated before significant confounders are selected by inspection of significance levels as well as impact of estimated coefficient for hypothesis variable.

Data and Safety Monitoring Plan:

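### The adjusted cost model lists adherence measured after randomisation as a covariate; separately, the event analysis is not tied to the GOLD strata and its 30- and 60-day horizons are not ranked

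*Combined protocol and SAP*

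**What the plan says.** Section VII plans recurrent-event methods: "We will use the count-approach and the gap-time approach", the former for event rates and the latter for time to occurrence, with every repeat hospitalization counted. On timing it says "Analysis will be performed for both 30- and 60-days". Section III defines the primary endpoint as "Composite end-point of time to occurrence of emergent healthcare utilization", with no horizon. Aim 2 concerns "therapy on the number of emergent and non-emergent healthcare utilization over 6 months".

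Section VII then turns to costs. It plans an unadjusted comparison by t-test or a non-parametric equivalent, and says that differences will be adjusted in "multivariate regression models, to include age, gender, race, body mass index, baseline severity of COPD, AVAPS-AE and medication adherence". After effect modification has been examined, "significant confounders are selected by inspection of significance levels" and by their impact on the coefficient of interest.

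Device adherence is described twice, both times for one arm: "One week Device Adherence Assessment (Intervention Group)" in Section VI (Post Discharge Study period) and "1 week PAP adherence assessment (Treatment Group only)" in the Study Process Flow table. Adequate adherence is defined as at least 4 hours on at least 5 of the first 7 nights. Section VI (Randomization) balances assignment within GOLD stages 2, 3 and 4 and caps stage 2 at 10 participants.

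**The concern.** A between-arm model should adjust only for what is fixed at randomisation. Device use comes later, is partly a result of assignment, and is not recorded for standard of care (SOC). Once it is in the model, the arm coefficient no longer estimates the effect of being assigned AVAPS-AE. With hours as the covariate it estimates the arm difference at zero use; with the binary definition, the difference between poor adherers and SOC. Two errors follow. Benefit delivered through use is assigned to the covariate, and if sicker patients use the device less, their higher costs are assigned to the arm.

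The selection rule does not protect against this. A covariate that overlaps heavily with the arm is likely to move the arm coefficient, which is one of the stated grounds for keeping it.

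Two smaller gaps concern events. GOLD stage governs the randomisation, but baseline COPD severity appears only in the covariate list that follows the costs, where selection could drop it. And day-30 and day-60 results can differ, with nothing to say which one answers the primary question.

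**Working it through.** **Inputs from the documents.** Section V: up to 80 enrolled, 60 completing, 25% attrition. This reproduces: 60/(1 - 0.25) = 80. No alpha, power or effect size is stated. Risks and Discomforts: expected 30-day readmission 20.5%.

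**Assumptions.** Two-sided 0.05; 30-40 per arm; mean use 3.9-4.9 h, SD 2.5 h; SOC use zero; correlation r between use and log cost of -0.2 to -0.3 (heavier users cost less). Use in SOC need not be zero, since sites that start PAP at once as usual care stay in the study, but no SOC download is described.

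**1. What the adjusted coefficient is.** With hours H = 0 throughout SOC, least squares on arm and H gives

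adjusted effect = unadjusted effect - b × mean(H),

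where b is the slope of log cost on hours within the intervention arm.

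**2. No true effect, hours as covariate.** In outcome SD units b = r/SD(H), so the bias is -r × mean(H)/SD(H). The ratio mean/SD is 3.9/2.5 = 1.56 to 4.9/2.5 = 1.96.
- r = -0.2: 0.2 × 1.56 = 0.31 to 0.2 × 1.96 = 0.39 SD of false harm.
- r = -0.3: 0.3 × 1.56 = 0.47 to 0.3 × 1.96 = 0.59 SD.
- r = 0: no bias, but the standard error grows by √[(2 + ratio²)/2] = 1.49 to 1.71.

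Rejection, smallest case (30 per arm, r = -0.2): SE = √(2/30) × 1.49 = 0.385; 0.31/0.385 = 0.81; about 13%. Largest case (40 per arm, r = -0.3): SE = √(2/40) × 1.71 = 0.382; 0.59/0.382 = 1.54; about 34%. Simulation gives 12-33%.

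**3. True benefit of 0.5 SD, hours as covariate.** If it works wholly through use, b × mean(H) = -0.5, so the adjusted effect is -0.5 + 0.5 = 0. Simulated power falls from 46-60% unadjusted to 5%. If half works through use, -0.25 SD remains, with power 8-12%.

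**4. Binary adherence.** The coefficient now compares poor adherers with SOC. With mean use of 4 h or more as a stand-in for the plan's rule, poor adherers average about half the arm's mean use, so both distortions roughly halve. False harm runs from 0.2 × 1.56 × 0.5 = 0.16 to 0.3 × 1.96 × 0.5 = 0.29 SD (simulated about 0.15-0.3 SD, 8-17% rejection). A 0.5 SD benefit wholly through use shrinks to about -0.25 to -0.27 SD.

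**5. Strata.** Simulated log-rank power at HR 0.5, with stage splits of 10/34/36 and 10/26/24 (only the cap of 10 is from the protocol). Stratified minus unstratified power is:
- stage not prognostic: -0.8 to 0.0 points;
- 1.5-fold hazard per stage: 0.2 to 1.4 points;
- 2-fold: 1.2 to 5.3 points.

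The unstratified test's size stays below 5% when stage is prognostic (4.4-4.9% at 1.5-fold, 3.6-4.3% at 2-fold).

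**6. Horizon.** At 20.5% by day 30 and a constant hazard, 60-day risk is 1 - 0.795² = 36.8%. If both arms had these rates, 60 patients give 60 × 0.205 = 12.3 and 60 × 0.368 = 22.1 events. Approximate log-rank power at HR 0.5 is Φ(0.693 × √12.3/2 - 1.96) = 23% and Φ(0.693 × √22.1/2 - 1.96) = 37%. In simulations at HR 0.5, with 60-day control risk 37% or 55%, the two horizons disagree in 17-27% of trials. The composite will be more frequent than readmission alone; its rate is not given.

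**The case against.** **Costs are secondary, and an unadjusted comparison is planned.** Both true. A reader might infer that adherence adjustment biases the primary time-to-event result. The text does not support that: the sentence on adjusting differences directly follows the cost comparison. The problem would reach the primary comparison only if the sentence were meant to cover events as well.

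**AVAPS-AE in the covariate list may mean the arm.** Possible. The device-use figures would then fall away. Medication adherence would remain. No measurement of it is described, but it is promoted by calls after discharge, so it too is most naturally post-randomisation. Its effect is not quantified here.

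**The larger adherence figures depend on coding.** This stands. The only adherence definition in the plan is binary, and it gives about half the distortion, so both sets are shown.

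**The plan does deal with repeat events.** This stands too. A reader might infer that a first-event rule is missing and that a first-event log-rank or Cox test should be primary. But the plan counts all repeat hospitalizations and chose methods that allow for a terminal event, so analysing all gaps is the plain reading. In simulation, switching to first events gives up 3-19 power points if the effect is equal in every gap, and the switch alone would leave death unaddressed.

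**Unranked horizons need not inflate error.** Testing at both days gives about 8% any-rejection under the null, but only under a rule that either result counts as success. The documents state no alpha and no such rule, and call the study a pilot. Nor does omitting the strata inflate error.

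**Conclusion.** The concern holds for the adjusted cost model as written. Adherence measured after randomisation, for device use in one arm only, does not belong in a between-arm comparison. Under a true null the false harm is about 0.3-0.6 SD (12-33% rejection) with continuous hours, or about 0.15-0.3 SD (8-17%) with the binary definition. A 0.5 SD benefit wholly through use shrinks to about 0 or about -0.25 SD respectively. These sizes rest on the assumed use levels, zero SOC use and a use-cost correlation of -0.2 to -0.3; with no correlation there is no bias under the null, only lost precision.

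The strata and horizon points are lesser matters of specification. The first costs about 0-5 power points if stage is 1.5- to 2-fold prognostic; the second leaves open which result answers the primary question. The documents do not support a claim that the primary result is biased or that its error rate is inflated.

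**What to change.** 1. Remove AVAPS-AE adherence and medication adherence from every between-arm adjusted model: costs, and events if the sentence is meant to cover them. If AVAPS-AE there denotes the arm, say so and keep it as the treatment term. Report adherence descriptively or in the per-protocol analysis already planned.
2. Include GOLD stage as randomised (2, 3, 4) in the event and cost comparisons, fixed in advance and exempt from significance-based selection.
3. Keep the planned recurrent-event methods: gap-time for the primary endpoint, counts for Aim 2, whose 6-month period needs reconciling with the 30- and 60-day analyses. A first-event analysis may be added as supportive, not substituted.
4. Name one horizon as primary and the other as supportive. Day 60 fits the 60-day therapy and study period; day 30 fits the readmission rationale in the background and the only stated event rate. The choice is the sponsor's.

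The cost is mainly wording. Stage is known at randomisation, and no extra participants or visits are needed. The downsides are under 1 power point lost if stage is not prognostic, and less freedom to choose among results.

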Participants who are screened for enrollment will be entered on a screening log which will be maintained at the clinical site. Participants referred for screening will be given a thorough explanation of the study and the requirements for participation by the study coordinator or other qualified medical professional. If the participant is interested in the study, the investigator or a member of his/her staff should approach the patient to obtain written informed consent. The background of the proposed study, the benefits and risks of the procedures and study should be thoroughly explained to the participant. The participant must sign the consent form prior to enrollment. This form or a modification of it must have prior approval of the study site's Institutional Review Board (IRB). Failure to provide informed consent renders the participant ineligible for the study.

Up to 10 sites will be recruiting for this study. Up to 80 participants will be enrolled across all sites with the goal of 60 participants (N=60) completing the study (25% attrition rate). One site should not enroll more than 25% of total N.

VI. Study Procedures

Screening Assessment

Hospitalized patients with comorbid COPD who are at high risk for readmission will be recruited. Specifically patients with comorbid COPD who are about to be discharged, with (a) prior hospitalization (within the past 12 months) Such participants will undergo questionnaire-based screening for sleep-disordered breathing (STOP-BANG questionnaire) and if they have a high risk for SDB (≥ 3 points) will undergo an overnight screening portable sleep study the night prior to hospital discharge (AHI ≥ 10 per hour; $>3\%$ oxygen desaturation for hypopneas). Sites may exercise the option of using the STOP-BANG questionnaire as a screening tool for the purposes of enriching the study population.

Spirometry

Each participant will undergo a spirometric assessment, using a handheld Koko™ unit, to determine if they meet inclusion criteria.

Spirometry will be performed based on the "Standardization of Spirometry – 2005".¹¹ Acceptability and reproducibility criteria are summarized in Table 8 of the ATS document. Spirometry equipment must be calibrated with a 3L syringe prior to the first use daily. The results will be printed and maintained in a calibration log, which will routinely be monitored for compliance during monitoring visits. Spirometry

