A Pilot, Multi-Center, Randomized, Open-Label, Parallel Group Study to Assess the Effects of a Novel Application of Averaged Volume Assured Pressure Support Ventilation (AVAPS-AE) therapy on Re-hospitalization in Patients with Sleep-Disordered Breathing with co-morbid COPD.

Confidential

intervention and SOC groups will receive \$150.00 as compensation for participating in the study. Compensation will be pro-rated based on completion of study milestones.

Information regarding admission, diagnostic tests, medication changes, and procedures will be collected from all participants. Discharge summaries of re-hospitalizations and office or ER visits and diagnostics tests and therapies received will be collected for measuring healthcare costs.

Participants will be asked if they would be interested enrolling in a registry for a 3 year follow-up. This will involve participants being contacted on a yearly basis inquiring about any hospitalizations, cardiovascular events, and assessment of vital statistics in the National Death Index registry. Participants who elect to enroll the registry will receive an additional \$25 in compensation.

Transition Plan:

Upon completion of the study or earlier termination, site investigators will cooperate with the study participants' primary health care providers regarding continuity of care to assure that participants receive appropriate follow-up care after the conclusion of the study. Study participants who are randomized to the treatment group, where a therapeutic benefit is evident, will be allowed to keep the provided AVAPS device until a similar replacement device can be provided to the participant through usual care pathways as part of this transition plan. Study participants who are randomized to the SOC group will have the option of receiving an AVAPS unit at the end of the 60 day period if prescribed and provided through the usual care pathway of their healthcare provider as part of this transition plan. The risk of additional and on-going device supplies not being covered by insurance or involving co-pays will be explained to the participant within the consent. Philips will not be responsible for providing device maintenance or study supplies after the 60 day study period.

Study Process Flow:

Study Procedures	Hospital Procedures (Pre-Discharge)	Post Discharge Study Procedures	Post 60 Day Study Procedures
Informed consent	X		
Inclusion/Exclusion Review	X		
Medical History Assessment	X		
Vitals	X		

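### Healthcare costs are compared by methods that ignore incomplete follow-up, although the plan allows for 25% attrition and does not say how a participant lost early is costed

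*Combined protocol and SAP*

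**What the plan says.** Section III lists healthcare costs first among the secondary endpoints. Section VII introduces the cost variable: "Actuarial costs will be assessed in patients belonging to both the intervention and usual care arm". It does not define actuarial costs. The comparison is then specified: "Unadjusted comparisons of these costs will be made by independent t-tests or non-parametric equivalent". Differences are next adjusted in "multivariate regression models, to include age, gender, race, body mass index, baseline severity of COPD, AVAPS-AE and medication adherence". That list has no follow-up time, offset or weight.

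The sentence just before the cost text sets the only time horizon in that section: "Analysis will be performed for both 30- and 60-days". Specific aim 2 in Section III speaks of utilization over six months and names re-hospitalization costs in the same sentence, so the cost window is not settled.

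For events, Section VII does provide for incomplete histories: "The method described by Cook and Lawless will be used to handle repeated hospitalizations, physician office visits, or emergency room visits in patients", and it goes on to allow for a terminal event. It does not extend this to the costs those events generate.

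On the source of cost data, the Day 60 text in Section VI says: "Discharge summaries of re-hospitalizations and office or ER visits and diagnostics tests and therapies received will be collected for measuring healthcare costs". On expected losses, Section V says: "Up to 80 participants will be enrolled across all sites with the goal of 60 participants (N=60) completing the study (25% attrition rate". The Data and Safety Monitoring Plan provides database codes for missing data but no rule for analysing it.

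**The concern.** A t-test, a rank test and an ordinary regression each need one cost figure per participant. Cost builds up over time, so a participant lost before Day 60 has a known cost only up to last contact. Two simple defaults are open, and the text permits either:

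- **Partial totals.** The cost seen so far stands in for the 60-day cost. Cost after last contact then counts as zero, and each arm's mean falls in line with the follow-up it has lost.
- **Completers only.** Participants lost early are left out. This selects on something that happens after randomisation, and it biases the comparison when dropout relates to cost.

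Neither default separates death, after which cost truly stops, from loss to follow-up, after which cost is unknown. Cost reduction is part of the rationale in the protocol's background. A reported saving, or the lack of one, could partly reflect how much follow-up each arm lost.

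**Working it through.** **1. The plan's own figure.** 60 / (1 − 0.25) = 80, and 80 × 0.75 = 60. The 80 enrolled, 60 completing and 25% in Section V agree. The documents give no cost standard deviation, no split of attrition by arm and no timing of dropout, so everything below rests on stated assumptions.

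**2. Partial totals.** Assume constant cost accrual over 60 days, no true cost difference, and dropout unrelated to cost. Let d be the dropout proportion in an arm and f the mean fraction of the 60 days observed among its dropouts. Then

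observed mean / true mean = 1 − d(1 − f).

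With uniform dropout (f = 1/2), and overall dropout after randomisation set at 25%:

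| AVAPS-AE v SOC dropout | Observed share, AVAPS-AE | Observed share, SOC | Apparent difference |
|---|---|---|---|
| 25% v 25% | 0.875 | 0.875 | 0% |
| 30% v 20% | 0.850 | 0.900 | 0.850/0.900 − 1 = −5.6% |
| 35% v 15% | 0.825 | 0.925 | 0.825/0.925 − 1 = −10.8% |
| 40% v 10% | 0.800 | 0.950 | 0.800/0.950 − 1 = −15.8% |
| 15% v 35% | 0.925 | 0.825 | 0.925/0.825 − 1 = +12.1% |

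With equal dropout, each arm's mean is 12.5% too low but the relative difference is not distorted.

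**3. Timing of dropout.** For 35% v 15%, early dropout (f = 1/3, mean day 20) gives 0.7667/0.9000 − 1 = −14.8%. Late dropout (f = 2/3, mean day 40) gives 0.8833/0.9500 − 1 = −7.0%. Over 30% v 20% to 40% v 10% and this range of f, the arm with more dropout looks cheaper by 3.6% to 21.4%.

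**4. Completers only.** Suppose dropouts would have cost r times what completers cost, with r the same in both arms. The completers' mean is then the true mean divided by 1 + d(r − 1). With equal true means, the apparent ratio is [1 + d_SOC(r − 1)] / [1 + d_AVAPS(r − 1)]. This equals 1 only if r = 1 or dropout is equal. If r differs between arms, equal dropout does not remove the bias either. The documents give no value for r.

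**5. Effect on the test.** A simulation used 20,000 trials, 40 participants per arm (equal allocation assumed), readmissions at the protocol's 20.5% 30-day rate, an assumed lognormal cost per event, and partial totals entered as full totals. Total rejection at the 5% level was 4.6% with no dropout, 5.3% at 35% v 15% and 5.8% at 40% v 10%. Rejections favouring the higher-dropout arm rose from 2.3% to 4.1% and 5.1%. Dividing cost by observed person-time brought the difference back to about 0% in every split simulated. Completers only also gave about 0%, but only because the simulated dropout was unrelated to cost.

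**The case against.** A reader might infer that the plan tests observed totals, so that early leavers count as cheap and AVAPS-AE will show a false saving. The documents do not support that reading, for these reasons:

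- **The method for incomplete costs is not stated.** Actuarial costs is undefined, and a completers analysis fits the stated goal of 60 completers equally well.
- **The 25% may not all fall after randomisation.** Section V ties enrolment to consent. Under Section VI, spirometry, a short sleep recording (with a replacement enrolled) and the wash-in can all still remove people. Losses before randomisation cannot bias the comparison between arms. Halving both rates in the 35% v 15% case gives (1 − 0.175 × 0.5)/(1 − 0.075 × 0.5) = 0.9125/0.9625, a false difference of 5.2% instead of 10.8%.
- **Unequal dropout is not forecast.** Section II describes the wash-in as a way to reduce attrition, which links intolerance of the therapy to loss. But stopping the device is not leaving follow-up: poor adherers stay in the intention-to-treat analysis. The imbalance could run in either direction.
- **Cost data may survive a missed call.** Costs come from discharge summaries and visit records, and Section II says deaths and hospitalizations are followed for at least 24 months.
- **The noise is large.** With 40 per arm, Poisson readmissions at the 20.5% rate and a per-event cost coefficient of variation of 0 to 1, the standard error of the difference is about 33% to 47% of mean cost. A bias of 5.6% to 15.8% is then about 0.1 to 0.5 standard errors, in a secondary endpoint of a pilot.

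All of this limits the size and direction that can be claimed. It does not supply a rule for incomplete costs, and the listed covariates do not correct for lost follow-up.

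**Conclusion.** The point holds as a conditional one. The plan names cost comparisons that take no account of incomplete follow-up, allows for 25% attrition, and provides for terminal events only in the event analysis. With partial totals, cost is understated and the comparison leans toward the arm that loses more participants. With completers only, it is biased if dropout relates to cost.

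The 5.6% and 10.8% figures are scenarios, not predictions. They assume the dropout split, uniform timing, constant accrual, and that the whole 25% falls after randomisation. The main harm is a biased cost estimate; the rise in false-positive tests is small. The primary endpoint is not affected. The plan should still be changed before analysis, because a better estimator is available at little cost.

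**What to change.** In Section VII:

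1. Define actuarial costs and a 60-day cost window, and reconcile that window with the six months in Specific aim 2.
2. Make the main cost analysis the difference in mean 60-day cost in all randomised participants, using a censoring-adjusted estimator. This can be interval-partitioned or inverse-probability-of-censoring weighted, split at Day 30 and Day 60, with baseline covariates in the censoring model.
3. Treat death as complete cost and loss to follow-up as censored. Where records can be obtained after a missed call, use them before declaring censoring.
4. Report a bootstrap 95% confidence interval, and follow-up time by arm.
5. Keep the t-test as a sensitivity analysis, and say whether it uses partial totals or completers.

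The cost is SAP wording, modest programming and possibly a somewhat wider interval. The estimator relies on censoring being non-informative given the modelled covariates. It does not cure dropout that depends on unmeasured drivers of cost, and the plan should say so.
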